6.3.10 Laboratory Evaluations

Clinical laboratory tests will be performed by a central laboratory specified and the laboratory's reference ranges will be used. The CTCC must be notified by the central laboratory during the study of any changes to the reference ranges. All samples for laboratory analysis must be collected, prepared, labeled, and shipped according to the laboratory's requirements. (Refer to instructions of the laboratory's manual.)

Blood samples will be collected at the Screening visit, Visits 06 and 08, and V10 (EOSD) or Premature Withdrawal Visit and Unscheduled visits (if clinically indicated) for the standard clinical safety laboratory analyses noted below. Retests may be performed if needed between visits for questionable results.

Clinical laboratory test results will be forwarded to individual Investigators and to the CTCC.

Clinical Laboratory Tests

Clinical Chemistry – albumin, alkaline phosphatase, aspartate transaminase (SGOT; AST), alanine transaminase (SGPT; ALT), bicarbonate, blood urea nitrogen (BUN), calcium, chloride, creatinine, glucose, lactate dehydrogenase (LDH), phosphate, potassium, sodium, total bilirubin, total creatine kinase (creatine phosphokinase), total protein, uric acid

Hematology – Hemoglobin, hematocrit, red blood cell count (RBC), platelet count, white blood cell count (WBC) with differential count (bands, monocytes, neutrophils, eosinophils, lymphocytes, basophils)

Urinalysis – pH, protein, glucose, ketone, blood microscopic, WBC count, RBC count, casts

Pregnancy Tests - Serum pregnancy test at Screening, Visits 06 and 08 and V10 (EOSD) or Premature Withdrawal Visits and Unscheduled visits (if clinically indicated). Preg-

nancy testing should be done for all women unless they are one year postmenopausal or surgically sterile. ***Any subject becoming pregnant during the study will be tapered from the study drug immediately. In addition, all attempts will be made to follow the subject until delivery.*** Any pregnancy that occurs during the study must be reported to the CTCC.

Laboratory reports from the central laboratory will be signed and dated by the site Investigator following review, and filed with the subject's source documents.

PK samples

Plasma PK samples will be collected at the Screening visit, Visits 03 (3 months) and 04 (6 months), or Premature Withdrawal Visit if it corresponds to Visits 03 or 04. The objective of collecting blood PK samples is to confirm isradipine trough concentrations and to establish a sparse PK profile of Isradipine IR based on the samples collected at 2-3 and 4-8 hours post dose windows. The data will be analyzed to demonstrate an appropriate level is achieved for the formulation used in this study and to address high inter-patient variability in serum concentrations to support the analysis in case variable results were observed. PK samples will be collected as outlined in Section 6.2.4 and shipped according to the laboratory's requirements. (Refer to instructions in the laboratory's manual.)

Plasma Biomarker samples

A blood sample will be collected from each subject at Screening, Month 36 (V10/EOSD) visits or at Premature Withdrawal visit and stored. These samples may be shared with other researchers for future unspecified research. Subjects will be given the option of refusing to have this sample collected, and their decision will not affect their participation in the study.

DNA Sample Collection

A blood sample will be collected from each subject at Screening and stored. These samples will be used to extract DNA for storage and shared for future unspecified research. Subjects will be given the option of refusing to have this sample collected or may request that their sample be destroyed at any time, without affecting their participation in the study. One of the rationales for the DNA sample collection is to assess if there is correlation of response to isradipine with a particular genetic profile.

6.3.11 Electrocardiogram (ECG)

A 12-lead resting ECG will be performed utilizing the central ECG laboratory equipment at Screening Visit, Visits 06, 08 and at the V10 (EOSD) or Premature Withdrawal visits. ECG will also be conducted at the Symptomatic Therapy visit if this visit is conducted in place of a regularly scheduled V06, V08 or V10. ECG readings/results will be provided by the Centralized cardiologist's interpretation.

Presence of 2nd or 3rd degree atrioventricular block will exclude the subjects from participation in the study. Investigator may consider other significant ECG abnormalities as the reason for exclusion for participation in study.

6.3.12 Additional Evaluations

Assess need for Symptomatic Treatment:

At each visit (except baseline), the Investigator will assess the subject's need for symptomatic treatment. A questionnaire will be used to facilitate the Investigator's decision. This decision will be based on PD disability posing a threat to the subject's current occupational status, current abilities (potential capacities) related to occupational matters, to handle routine personal finances and domestic responsibilities, and activities of daily living.

6.3.13 Adherence Assessments

At each study visit, the site Investigator and/or Study Coordinator will assess the subject's adherence with the study requirements. This will include checks of protocol compliance, concomitant medication use, blood pressure recordings, and use of study drug in order to assess the reliability of subject-generated data. In extreme circumstances, subjects who consistently fail to comply with the study requirements may be withdrawn from the study.

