5.4 Study Drug Reductions

Dosage reductions can occur at any time during the study. Random dose adjustments may be done in both study groups (active or placebo) at the direction of the Biostatistician at the University of Rochester in order to preserve the study blinding. In case of intolerability, dosage reduction should be attempted prior to discontinuing study drug. Instructions for dosage reduction may be given either over the phone after review of the adverse events or at the corresponding in-person visit (either regularly scheduled or unscheduled visit depending on the timing of the dosage reduction). See below for dosage reduction directions. **For individuals on concomitant anti-hypertensive medication with adverse events referable to hypotension, reduction in the anti-hypertensive agent should be undertaken first** (see 5.2.7 #7 above).

Subjects will reduce their dosage in a blinded fashion by 1 capsule (equivalent to 2.5 mg of Isradipine IR or placebo) each week. Dosage reduction should start by withdrawing a capsule from AM dose if on 10mg daily dosing (2 capsules twice daily). Subjects unable to tolerate 7.5mg dosage (one capsule in AM and two capsules in the evening daily) after a week will be instructed to reduce the dosage further to one capsule twice daily (equivalent to 5 mg Isradipine IR or placebo daily). Subjects unable to tolerate 5 mg daily dosage after a week will be instructed to reduce the dosage further to one capsule once daily taken in PM (equivalent to 2.5 mg Isradipine IR or placebo daily). Subjects unable to tolerate 2.5 mg daily dose will be taken off the study drug. In accordance with the intent-to-treat principle these subjects will be encouraged to remain in the study and every attempt will be made to continue to follow them and obtain the primary outcome data.

All study drug reductions must be called to the CTCC.

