5.8 Adherence Assessment

AT EACH STUDY VISIT, THE SITE INVESTIGATOR AND/OR STUDY COORDINATOR WILL ASSESS THE SUBJECT'S ADHERENCE WITH THE STUDY REQUIREMENTS. THIS WILL INCLUDE CHECKS OF PROTOCOL COMPLIANCE, CONCOMITANT MEDICATION USE, BLOOD PRESSURE RECORDS, AND USE OF STUDY DRUG IN ORDER TO ASSESS THE RELIABILITY OF SUBJECT-GENERATED DATA. USE OF STUDY DRUG (PILL COUNTS) WILL BE ASSESSED AT VISIT 01 AND EVERY SCHEDULED DRUG RETURN VISIT THEREAFTER. IN EXTREME CIRCUMSTANCES SUBJECTS WHO CONSISTENTLY FAIL TO COMPLY WITH THE STUDY REQUIREMENTS MAY BE WITHDRAWN FROM THE STUDY. 6 CLINICAL AND LABORATORY EVALUATIONS

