6.2.11 Premature Withdrawal Visit (PW)

Subjects have the right to withdraw from the study at any time without prejudice. In the event of premature study withdrawal (either subject or Investigator initiated), a Premature Withdrawal visit should occur. **All efforts should be made to conduct the PW visit prior to study drug discontinuation.**

Reasons for withdrawal of the subject prior to completion of the study must be stated in the CRF and in the site source documentation for all study subjects who were enrolled in the study. ***The CTCC must be informed by telephone within 24 hours of all study subjects who are withdrawn from the study.***

At the time of the premature withdrawal visit, subjects should be instructed to taper their study drug if applicable. Subjects will taper their dosage by 5 mg of Isradipine IR or placebo to one capsule twice daily every 2 days). If a subject has already decreased their dosage due to prior intolerability to 5mg or below, then they will discontinue the drug at the start of the taper. The subject should be instructed to take the study drug (with or without food) in the morning () and in the evening.

Written directions for drug tapering should be given to the subject. Visit 11 activities should be performed at that time.

Every effort should be made to keep each subject in the study. Subjects coming off study drug should be encouraged to continue in the study, off study drug. However, all subjects must present for a final (V10 or PW) in-person visit.

Procedures & Evaluations:

- General Neurological Exam
- General Physical Exam
- Concomitant Medication Log
- Columbia Suicide Severity Rating Scale (C-SSRS)
- Beck Depression Inventory II (BDI-II)
- Montreal Cognitive Assessment scale (MoCA)
- Assess primary diagnosis/probability of PD
- Vital Signs (blood pressure, heart rate, temperature, weight)
- Safety Laboratory tests (serum chemistry, hematology, urinalysis)
- Plasma PK sample - To be done only if premature withdrawal corresponds to Visits 3 or 4 (see instructions Section 6.2.4)
- Plasma sample for storage for future potential biomarker studies (only for subjects who consented for biomarker sampling)
- Serum pregnancy test - Complete all women unless they are one year postmenopausal or surgically sterile
- Modified Rankin Scale
- Exercise Questionnaire
- Electrocardiogram (12-lead ECG)
- PD Quality of Life Scale (PDQ-39)
- Quality of Life in Neurological Diseases (Neuro-QOL)

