8.2 Outcomes

8.2.1 Primary Outcome

Efficacy:

Efficacy will be defined as the change in total UPDRS score between the baseline visit and month 36. Comparison will be made between active treatment arm and placebo. We expect that nearly all subjects will require symptomatic therapy (e.g. levodopa or dopamine agonist) prior to the end of the 36 months study. In that case UPDRS will be assessed in the medications ON state (based on the subject/ investigator defined BEST ON, approximately 1 hour after dose of symptomatic therapy).

Medications ON state was chosen based on the following rationale: if disease modifying effect of isradipine exists it will be sustained even in the medications ON state; the practical difficulty in withdrawing subjects; the persistent symptomatic benefit of symptomatic therapy even in the “defined medications OFF” state. In addition there are no pilot data on the longitudinal change of UPDRS in the medications OFF state over 36 months period in de novo population to allow power calculations.

Our primary efficacy analysis will use analysis of covariance applied to the change from baseline in the total UPDRS score. The baseline value will be entered into the model as a continuous variable, the assigned treatment and the enrolling Investigator will be entered as a stratification variable. The primary analysis will be based on the intent-to-treat principle and will include all subjects who have 36 month data. A two-sided test with $\alpha = 0.05$ will be used to declare statistical significance. Sensitivity analyses will be performed using data values imputed under various “missingness” mechanisms for the subjects who do not complete 36 months of follow-up. Consistency of results over study sites and with respect to major demographic and clinical baseline variables will be assessed descriptively and by appropriate tests of statistical interaction. We will also perform an exploratory analysis by achieved final dosage (0, 2.5, 5.0, 7.5 and 10.0) for the subjects assigned to active treatment.

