A. *Intent-to-Treat.* Efficacy analyses will use the intent-to-treat principle, whereby all subjects are kept in their assigned treatment groups for statistical analysis, even if they discontinue study medication or continue on a reduced dosage. Subjects who discontinue study medication will be encouraged to remain in the study and their data will be used in the primary efficacy analysis. Subjects who have no post-baseline efficacy data will be excluded from the primary analysis as their primary outcome variable will be missing. The primary analysis will compare the active treatment group (all subjects randomized to receive active isradipine) to the placebo group. All P-values for efficacy outcomes will be two-sided.

B. *Baseline Characteristics.* Demographic and clinical characteristics, including age, gender, race and ethnicity, years of education, time since PD diagnosis, UPDRS score at entry including its mental, motor and ADL components, MDS-UPDRS, Modified Rankin Score, Modified Hoehn and Yahr score, PDQ-39 score, MOCA score (adjusted for education level) of the two treatment groups will be presented. Systolic and Diastolic blood pressure and other vital signs data will also be shown.

C. *Subject Disposition.* Losses to follow-up, compliance to study medication, protocol violations and other notifiable incidents will be tabulated. A CONSORT type diagram showing the progress of all enrolled subjects through the study will be prepared.

(Numbers of subjects screened but ineligible, and those eligible but not enrolled, will be provided by the CTCC).

3. Primary Efficacy Analysis

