A. Outcome Variable. The pre-specified primary outcome variable will be the change from baseline to the three-year follow-up visit in the total score from Parts I, II and III of the UPDRS score (mental, motor and ADL components). We anticipate that by the three year visit a substantial majority of participants will be receiving symptomatic medication. Unlike in previous studies in early PD (e.g. DATATOP, PRECEPT, QE3)[1-3] subjects who require symptomatic treatment (typically levodopa or dopamine agonists) during the course of the study will continue in the study, receiving their assigned study medication. By this strategy we hope to minimize drop-outs. For subjects receiving symptomatic medication the UPDRS will be assessed in the ON state, based on the subject/ investigator defined BEST ON, approximately 1 hour after dose of symptomatic therapy). Subjects who do not complete the three-year visit will have their primary outcome variable set to missing; a variety of sensitivity analyses (see below) will be conducted to assess the influence of these subjects on the primary analysis.

B. Statistical Model. The primary analysis will use analysis of covariance applied to the change from baseline in the total UPDRS score. The baseline value will also be entered into the model as a continuous variable, the assigned treatment and enrolling site will be entered as categorical variables. A two-tailed test with $\alpha = 0.05$ will be used to declare statistical significance.

C. Adjustments to the Analysis. (i) It may occasionally happen that certain items on the UPDRS are missing at a particular visit, for example if a subject is unable to perform a test due to injury. To enable the valid data from that visit for that subject to be used in the analysis, single missing items on the UPDRS will be carried forward from the subject's previous visit. A maximum of five missing items may be carried forward in this way, including from the baseline visit to the one-month visit if necessary. Items missing at baseline may be carried forward from the screening visit. (ii) For analyses that include the enrolling site as a stratification factor, sites that enroll fewer than four subjects will be combined to form a single "super-site".

4. Secondary Efficacy Analyses

A. 36-month data. The changes from baseline to 36 months in the following measures of disability will be analyzed in a similar fashion as that for the primary outcome variable

I. Motor disability

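### The non-compliance clause permits withdrawal from the study, not only from study drug, and so can create avoidable missing Month-36 outcomes

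*Protocol*

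**What the plan says.** **The clause.** Protocol 5.8 and 6.3.13 have site staff check adherence at each visit: protocol compliance, concomitant medication, blood pressure records and use of study drug. Section 6.3.13 then says: "In extreme circumstances, subjects who consistently fail to comply with the study requirements may be withdrawn from the study". Section 5.8 gives the same permission: "SUBJECTS WHO CONSISTENTLY FAIL TO COMPLY WITH THE STUDY REQUIREMENTS MAY BE WITHDRAWN FROM THE STUDY". Neither section sets a threshold, names who decides, or says whether the subject is still seen at Month 36.

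**What follows withdrawal.** Protocol 6.2.11 states: "In the event of premature study withdrawal (either subject or Investigator initiated), a Premature Withdrawal visit should occur". That visit includes the UPDRS. The reason for withdrawal is recorded and the coordinating center is told within 24 hours.

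**The primary analysis.** SAP 3.A: "Subjects who do not complete the three-year visit will have their primary outcome variable set to missing". Under Protocol 8.2.1 the primary analysis follows intent-to-treat and "will include all subjects who have 36 month data".

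**Retention elsewhere.**
- Protocol 5.4, on subjects who cannot tolerate the lowest dose: "these subjects will be encouraged to remain in the study and every attempt will be made to continue to follow them". Section 5.2.5 treats subjects whose assignment was disclosed in the same way.
- Protocol 5.7.2 has subjects who need a disallowed medication followed off study drug.
- Protocol 6.2.11: "Every effort should be made to keep each subject in the study".
- SAP 2.A: "Subjects who discontinue study medication will be encouraged to remain in the study and their data will be used in the primary efficacy analysis".
- Protocol 8.5, under non-compliance, keeps all subjects in the primary analysis by intent-to-treat. Subjects not taking drug correctly are removed only to test sensitivity.

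**The concern.** Elsewhere the plan separates stopping study drug from leaving the study, so that the Month-36 UPDRS is obtained whatever happens to treatment. The non-compliance clause does not make that separation. It allows a subject to be taken out of the study after randomization because of behaviour that treatment or disease may influence.

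A link to treatment is plausible. In the pilot study (Protocol 2.6), peripheral edema was reported by 34.62% at 10 mg and 3.85% on placebo, and 73% and 96% respectively completed without a dosage adjustment. Some subjects with side effects will have their dose formally reduced; others may simply take drug irregularly. Worsening disease could also reduce compliance in either arm. If such subjects are withdrawn, the completers are a selected group and the selection may differ by arm.

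The clause also weakens the comparison planned in Protocol 8.5. Analysing with and without non-compliant subjects tells less if the most non-compliant have already left and have no Month-36 value.

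**Working it through.** **Step 1: follow one subject through the plan.** Persistent non-compliance (5.8, 6.3.13) can lead to withdrawal from the study and a Premature Withdrawal visit (6.2.11). With no Month-36 visit, the outcome is set to missing (SAP 3.A) and the subject is absent from the ANCOVA (8.2.1). The withdrawal-visit UPDRS does not take its place there. Protocol 8.5 does carry a whole previous visit forward when more than five UPDRS items are missing, which does not fit neatly with SAP 3.A. I follow the SAP, which caps carried-forward items at five and sets the outcome to missing.

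**Step 2: reproduce the sample size.** Inputs from Protocol 8.3: difference 4, SD 12.0, two-sided alpha 0.05, power 80%, dropout 15%.
- n per arm = 2 × (1.960 + 0.842)² × 12² / 4² = 141.3, rounded up to 142.
- 142 / 0.85 = 167.1, rounded up to 168 per arm, or 336 in total. This matches.
- Evaluable per arm: 168 × 0.85 = 142.8. SE of the difference = 12 × √(2/142.8) = 1.42. Power = Φ(4/1.42 − 1.96) = 80.4%.

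The withdrawal table in SAP section 7 also reproduces. At 20% withdrawal: 78.0% power, 4.10 points, and 336 × 0.85/0.80 = 357, or 21 more subjects. At 25%: 75.4%, 4.24 points, and 336 × 0.85/0.75 = 380.8, or 45 more.

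**Step 3: effect on power.** The documents give no rate of withdrawal for non-compliance. I assume 1 to 5 percentage points, and evaluate power at 168 × (1 − missing fraction) per arm.

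| Assumption | Missing | Power |
|---|---|---|
| Stated design | 15% | 80.4% |
| 1 point of the 15% is retained instead | 14% | 80.9% |
| 5 points of the 15% are retained instead | 10% | 82.6% |
| 1 point on top of the 15% | 16% | 80.0% |
| 3 points on top | 18% | 79.0% |
| 5 points on top | 20% | 78.0% |

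**Step 4: effect on the estimate.** Suppose about 143 subjects in an arm would otherwise give Month-36 data. Let k be the net excess removed from that arm compared with the other, and d the difference between their mean change and that of the rest of the arm. Dropping them moves the arm mean by k × d / 143. Both k and d are assumed.

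| k | d (points) | Shift (points) | Share of 4 points |
|---|---|---|---|
| 3 | 5 | 15/143 = 0.10 | 3% |
| 5 | 8 | 40/143 = 0.28 | 7% |
| 8 | 10 | 80/143 = 0.56 | 14% |

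As a cross-check with other assumed inputs, removing 1% to 5% of one arm with d between 4 and 12 gives 0.01 × 4 = 0.04 to 0.05 × 12 = 0.60 points. Even the largest shift in the table is 0.56/1.42 = 0.39 of a standard error.

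**The case against.** The case for leaving the text alone has real weight.

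- **The clause is narrow.** It is permissive and reserved for consistent failure in extreme circumstances.
- **The retention text is best-efforts wording.** It speaks of encouraging subjects and making every attempt. Section 6.2.11, which asks that each subject be kept, also recognises withdrawal initiated by the investigator. The passages on disclosure, intolerability and needed medication each cover their own situation, not general non-compliance.
- **Side effects already have a route.** Intolerability leads to dose reduction and then follow-up off drug. Nothing tells a site to withdraw someone who misses capsules because of edema.
- **Few subjects may be affected.** Pilot compliance by pill count was 99.94%, and 8 of 99 subjects terminated early for any reason, 5 of them in the 20 mg group.
- **Missing data are planned for.** There is a 15% allowance, and the plan specifies multiple imputation, best- and worst-case analyses, mixed models (SAP 4.C) and imputation from the subject's history at termination (Protocol 8.5).

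Most of this stands, and it limits the size of the point. It does not remove it. The pilot lasted 52 weeks and used the CR formulation, so it is indirect evidence for 36 months on IR. The sensitivity analyses show how much a missing outcome could matter; they do not supply it. And nothing in 5.8 or 6.3.13 directs the site to Protocol 8.5 or to a Month-36 assessment.

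**Conclusion.** The point holds as a small but avoidable weakness. Sections 5.8 and 6.3.13 permit withdrawal from the study for persistent non-compliance, and without a Month-36 visit that subject is lost to the primary ANCOVA. This is in tension with Protocol 6.2.11, Protocol 8.5 and SAP 2.A, and the resulting missingness may be informative. Under the assumed inputs the shift is about 0.1 to 0.6 points. No frequency is stated, and no design figure is wrong.

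A reader might infer more, and the documents do not support it:
- **A strict contradiction.** No passage guarantees that every subject off drug is followed to the end. The conflict is one of intent, left unreconciled.
- **A site's free hand to remove anyone who skips capsules.** The clause is confined to extreme cases and names no decision-maker. The site makes the adherence assessment, and investigator-initiated withdrawal is recognised, but sole site authority is an inference.
- **An expected bias of 3% to 14% of the target effect.** Those percentages come wholly from assumed numbers and directions of removal. They illustrate scale; they are not an estimate.
- **A rule that only withdrawn consent, death or loss to follow-up may end participation.** The intent-to-treat text does not imply this. It would conflict with investigator-initiated withdrawal in 6.2.11 and with the joint decision on suicidal subjects in 6.3.9.

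**What to change.** In 5.8 and 6.3.13, replace the withdrawal sentence with one to this effect: *Non-compliance alone does not end study follow-up. The subject is encouraged to remain in the study, on or off study drug under the existing rules, and every attempt is made to obtain the Month-36 UPDRS.* This brings both sections into line with Protocol 6.2.11, Protocol 8.5 and SAP 2.A.

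Leave investigator-initiated withdrawal (6.2.11) and the participation decision for suicidal subjects (6.3.9) unchanged for other reasons. No dosing rule, study procedure or sample size changes.

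The cost is one sentence in each of two sections, plus continued contact with a few difficult subjects, whose data may be less reliable. Protocol 8.5 already provides for that concern by repeating the primary analysis without subjects who did not take study drug correctly.
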